# **5. ABSTRACT**

None

# 6. MILESTONES

Milestone	Planned date
Start of data collection	01 December 2022
End of data collection	28 March 2023
Final study report	15 June 2023

# 7. RATIONALE AND BACKGROUND

B-cell acute lymphoblastic leukemia (ALL) is a malignant transformation and proliferation of lymphoid progenitor cells in the bone marrow, blood, and extramedullary sites. Only 20% of ALL occurs in adult patients.iii Incidence data on adult B-cell ALL in India is lacking.iv The regimens used for pediatric patients with B-cell ALL are mostly used for the treatment of adult patients with B-cell ALL. The treatment of B-cell ALL in adults is mostly based on regimens developed for pediatric patients.

Most chemotherapy regimens used to treat adults with B-cell ALL in India consists of multi-agent induction, intensification or consolidation, and maintenance phases, together with central nervous system (CNS) prophylaxis using intrathecal chemotherapy, with or without cranial irradiation. Commonly used cytotoxic agents in first line treatment protocol for adult patients with B-cell ALL are cyclophosphamide, vincristine, daunorubicin, L-asparaginase and prednisolone. The prognosis of R/R B-cell ALL has historically been dismal with complete remission (CR) rates of 20-40%, median OS of 6 months, and cure rates of < 10% even with intensive salvage chemotherapy and HSCTv.

R/R B-cell ALL in adults is a challenging disease, with high mortality resulting from refractory disease or toxicity from intensive chemotherapy regimens. The only curative option in this subset of patients is CR after salvage therapy followed by allo-HCT. Even salvage regimens in case of relapse are mostly composed of old agents used in first-line protocols. Although second remissions are possible, with these salvage regimes, these are of short duration unless an allogeneic stem cell transplant is feasible.vi The data on the outcomes of salvage therapy in adult patients with B-cell ALL is lacking from India. However, Novel therapies such as InO have improved the outcomes of this subset of patients, with more patients experiencing CR and minimal residual disease negativity, thus becoming eligible for allo-HCT. The real-world data on the use of Ino monotherapy in cases of adult R/R B cell ALL is limited in Indian settings with knowledge gaps relating to diagnostic and treatment practices. Currently, only a single study is available with CUP data from 8 patients.

InO is an antibody-drug conjugate consisting of a recombinant, humanized IgG4 antibody (G544) covalently bound to a semi synthetic derivative of calicheamicin. Calicheamicin, a cytotoxic natural product produced by microbial fermentation that is significantly more potent than conventional cytotoxic chemotherapeutic agents, binds to the DNA minor groove and causes cell death by inducing double strand DNA breaks. The targeting agent in InO, (G544) specifically recognizes human CD22, which is expressed on the malignant cells of the majority of B-lymphocyte malignancies, including on the surface of blasts in >90% of patients with B cell ALL.vii In 2017, the United States (US) Food and Drug Administration (FDA) and European Medicines Agency (EMA) approved InO for the treatment of adult with R/R B-cell precursor B-cell ALL.viii,ix

#### Inotuzumab: mode of action and literature evidence

ALL is the second most common acute leukemia in adults. The characteristic features are chromosomal abnormalities and genetic alterations involved in differentiation and proliferation of lymphoid precursor cells. The backbone of therapy remains multi-agent chemotherapy with

#### PFIZER CONFIDENTIAL

CT24-WI-GL02-RF02 4.0 Non-Interventional Study Protocol Template For Secondary Data Collection Study 01-Jun-2022 Page 12 of 24 vincristine, corticosteroids and an anthracycline with allogeneic stem cell transplantation for eligible candidates.x

The advent of moAb targeting CD22 (InO) and CD19 (blinatumomab), have dramatically improved the outcome of adults with R/R B cell ALL. These have shown significant survival benefits against standard therapies and expanded the armamentarium of ALL.xi

InO is an anti-CD22 moAb conjugated to the cytotoxic antibiotic calicheamicin. Based on promising phase I/II data, InO was compared to standard salvage chemotherapy in Phase 3 multicenter trial (INO-VATE) of 218 adult patients with CD22+ B cell ALL. The overall response and MRD negativity rates among responders were significantly higher with InO compared with chemotherapy (81% versus 29%, p < 0.001, and 78% versus 28%, p < 0.001, respectively). More patients who received InO were able to undergo HSCT (41% versus 11%; p < 0.001). The median remission duration and progression-free survival were significantly longer with InO (4.6 versus 3.1 months; p = 0.03, and 5.0 versus 1.8 months; p < 0.001, respectively). The median OS was 7.7 versus 6.7 months (p = 0.04). This was later confirmed with longer follow-up on 326 patients showing 2-year OS rates of 23% versus 10% (p = 0.01) in favor of InO [24]. Predictors for better survival included achievement of CR, MRD negativity, and consolidative HSCT. Patients who achieved MRD negativity derived more benefits regardless of the number of prior therapies.xii

InO is an ADC comprising of a moAb targeting CD22,xiii a cell surface antigen expressed on approximately 90% of B-cell malignancies,xiv linked to a cytotoxic agent.

CD22 is an important modulator of B-cell lymphocyte function and survival,xv and is expressed on mature B-cells, which may allow for targeted delivery of the cytotoxic agent.xvi

When InO binds to the CD22 antigen on malignant B-cells, it is absorbed into the cell, at which point the cytotoxic agent calicheamicin is released to destroy the cell.xvii

Adding an ADC targeting CD22, such as InO, to existing treatments options, may provide additional anti-tumor activity.xviii

# 8. RESEARCH QUESTION AND OBJECTIVES

We aim to carry out a multicentric retrospective cohort analysis study with data from approximately 55 patients to observe clinical outcomes among patients treated with InO monotherapy in real-world clinical practice in India.

# 9. RESEARCH METHODS

This research is designed as a multicenter, retrospective study. Site investigators, namely hematologists /oncologists who are experienced in treating hematological malignancies in India will drive this research.

## 9.1. Study design /Setting

The study is classified as a Non-interventional study (NIS) secondary data collection- unstructured review with sites/investigators.

R/R B-cell ALL patients who are 18 years old at the time of InO initiation and those who received the drug outside of clinical trials will be evaluated.

Data will be collected retrospectively from patients hospital medical records (paper-based ) by members of the direct care team (investigators). We intend to have 7- 10 sites across India using InO monotherapy including patients with both private purchase and compassionate use to reach a cohort of approximately 55. If needed, more sites will be enrolled to meet the target cohort. Data will be reviewed and analyzed from all the sites.

Medical records will be reviewed to collect demographic, patient-related, disease-related, and clinical outcome data. These patients will be evaluated for response (CR/CRi), MRD status, duration of remission (DOR), Dosage patterns, Rate of transplant, Overall survival in all patients including Survival rate at 6 months and 12 months in transplanted patients & non transplanted patients, Relapse free survival (RFS), Rate of VOD (Total, during study treatment and post HSCT if any patient underwent HSCT), safety/tolerability, Other adverse effects (including hematological toxicities and raised liver enzymes), No of cycles to achieve MRD negativity in responders & CR/CRi in EMD/LBL.

#### 9.1.1. Inclusion criteria

- Patients must meet all of the following inclusion criteria to be eligible for inclusion in the study:
- Patient Population -
- Patients aged ≥18 years old at the initiation of InO treatment
- Patients with relapsed/refractory B-cell ALL
- Patients who initiated InO monotherapy between Feb'2017 and Feb'2022 and are CD22 positive
- Ph+ patients who have failed treatment with at least 1 TKI

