# **3. KEY DEFINITIONS**

Index date: The date of initiation of the first cycle of InO.

**Baseline period**: Period from 6 months before index date to the index date. The closest observation recorded during the baseline period and closest to index date will be used as baseline data (when more than one observations are available).

**CR/CRi rate**: Number of patients who achieve complete remission/complete remission with incomplete hematologic recovery (CR/Cri) divided by the total number of patients completing treatment with InO (defined as patients with a recorded date of discontinuation of InO).

**Complete remission (CR)**: is defined as 5% bone marrow blasts, no evidence of disease in the bone marrow, and recovery of peripheral blood count (platelet count of >  $100 \times 109/L$  and absolute neutrophil count of >  $1 \times 109/L$ ).

**CR with incomplete count recovery (CRi)**: is defined as 5% bone marrow blasts and no evidence of disease in the bone marrow, but with incomplete recovery of peripheral blood count. Minimal residual disease (MRD) will be assessed at each participating institution by multicolor flow cytometry.

**MRD negativity r**ate: Proportion of patients in whom minimal residual disease (MRD)-negative status is observed, among patients in whom MRD negativity status has been assessed, at any time until the end of treatment with InO (defined as the date of recorded discontinuation of InO). OS: Time from index date to death.

**RFS:** Time from index date to the earliest date of the following events: death, progressive disease (including objective progression, relapse from CR/CRi, treatment discontinuation due to global deterioration of health status), or the start of new induction therapy or posttherapy haematopoietic stem cell transplantation (HSCT) without achieving CR/CRi.

**EMD**: Extramedullary disease is the presence of leukemic cell aggregates in the form of solid tumor outside that of bone marrow.i

LBL: lymphoblastic lymphoma, is a clonal hematopoietic stem cell disorder of B or T cell originii

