#### 9.1.2. Exclusion criteria

- Patient not completing at least 1 cycle of InO therapy
- Patient on InO in combination with chemotherapy

Following local legislation, informed consent won't be signed by the patients since this is a retrospective study and they are not getting enrolled in a prospective clinical trial. All data points mentioned in the inclusion criteria should be available which are necessary to analyze protocol endpoints for the selected patient cohort who has undergone the full treatment of the drug in question. Ethics Committee approval of study protocol will be taken to access medical records.

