### 9.1.3. Primary endpoint

Complete remission or complete remission with incomplete hematological recovery following treatment with InO, by the number of salvage therapies  $(0, 1, \ge 2)$  received before InO initiation.

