#### All these parameters will be assessed in the following subgroups -

- 1st salvage and later lines
- High burden and Low burden disease (<50%; 50-90%; >90%)
- Ph +ve and Ph ve patients
- Elderly patients> 65 years

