# 5.1 EFFICACY/EFFECTIVENESS ENDPOINT(S)

The primary outcomes of interest are CR/CRi achieved or not following InO treatment which will be measured by binary response and duration of remission which will be measured by time to achieve CR/Cri from InO therapy starts. Other secondary outcomes will be measured by binary response mostly, but time to event for dealth and relapse will be measured by time from starting of the therapy to the event of interest. The longest time from initiation of InO to date of data extracted will be considered as study period. The number of salvage therapies received prior to the InO therapy initiation will be classified into 0, 1 and >1.

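### The primary CR/CRi rate does not require marrow disease when InO starts, so a patient whose marrow is already clear at index can count as a responder

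*Protocol*

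**What the plan says.** **Entry.** Protocol 9.1.1, repeated in SAP 4.1, lists age, "Patients with relapsed/refractory B-cell ALL", CD22 positivity, InO monotherapy started in the window, and TKI failure for Ph+ patients. Relapsed and refractory are not defined, and no marrow finding at index is required. Of the two exclusions in Protocol 9.1.2, one is "Patient not completing at least 1 cycle of InO therapy" and the other is combination with chemotherapy. Neither removes a patient in marrow remission at index.

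**Response.** In Protocol section 3, CR "is defined as 5% bone marrow blasts, no evidence of disease in the bone marrow, and recovery of peripheral blood count". CRi "is defined as 5% bone marrow blasts and no evidence of disease in the bone marrow, but with incomplete recovery of peripheral blood count". (The comparison sign before 5% is taken as lost when the PDF was read.) Neither definition refers to the baseline marrow. SAP Appendix A1.2, reserved for further endpoint definitions, is empty.

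**Endpoint and denominator.** The primary endpoint in Protocol 9.1.3 is "Complete remission or complete remission with incomplete hematological recovery following treatment with InO", by number of prior salvage therapies. Protocol section 3 has the responders "divided by the total number of patients completing treatment with InO", meaning those with a recorded discontinuation date.

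**Baseline and scope.** The baseline period runs back 6 months from the first cycle, and the record closest to index is used (Protocol section 3). The burden subgroups are "High burden and Low burden disease (<50%; 50-90%; >90%)", so the lowest class has no floor. Response in EMD/LBL is a secondary endpoint (Protocol 9.1.4), so such patients are expected in the cohort.

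**The concern.** A remission rate is read as the share of patients whom the drug brought into remission. That reading needs every patient in the denominator to be out of marrow remission at the start. A trial with a screening marrow usually secures this at entry. This chart review does not, and the response definition does not make up for it.

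The foreseeable cases are a patient with isolated EMD or LBL and a clear marrow, and a patient whose marrow was cleared by other treatment during the baseline window. If nothing changes in the marrow, the next examination meets the CR or CRi definition.

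The effect would reach beyond the overall rate:
- The comparison across salvage strata is distorted if the share of already-clear patients differs between 0, 1 and ≥2 prior salvage therapies.
- Time to CR/CRi (SAP 5.1) and cycles to CR/CRi (Protocol 9.1.4) are shortened.
- RFS changes, because its definition uses CR/CRi status to decide whether a transplant or new induction counts as an event.

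**Working it through.** The plan has no figure to reproduce. The sample size (32 under the administrative change letter, about 55 before it) rests on available records, with no power, precision or null rate. The check is a reading of the rule followed by a bias calculation.

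**Step 1: trace a patient with a clear marrow at index.** The patient has relapsed disease outside the marrow, is an adult, is CD22 positive, completes one cycle and later stops InO.
- Inclusion and exclusion: passes as written.
- Denominator: counted, since a discontinuation date is recorded.
- Later marrow, unchanged: below the limit, with no evidence of marrow disease. It scores CR if counts are recovered and CRi if not.

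The patient can be a primary responder with no change in the marrow.

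**Step 2: size.** Let f be the share already clear at index, q the rate at which they are scored responders, and p the true rate in the rest.

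Reported rate = f·q + (1−f)·p, so bias = f(q−p). If all are scored responders (q=1), bias = f(1−p).

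Inputs:
- p = 40% is the top of the historical CR range of 20–40% for R/R disease (Protocol section 7).
- p = 81% is the InO response rate quoted there from the phase 3 trial.
- f is not in the documents. 5% to 30% is assumed.

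| f (assumed) | p = 40% | p = 81% |
|---|---|---|
| 5% | 0.05×0.60 = 3.0 points | 0.05×0.19 ≈ 0.9 points |
| 10% | 0.10×0.60 = 6.0 | 0.10×0.19 = 1.9 |
| 20% | 0.20×0.60 = 12.0 | 0.20×0.19 = 3.8 |
| 30% | 0.30×0.60 = 18.0 | 0.30×0.19 = 5.7 |

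**Step 3: in patients, at N=32.** Exact (Clopper-Pearson) 95% intervals; the numbers already clear are assumed.

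| Already clear | True rate near | All patients | Marrow disease at index only |
|---|---|---|---|
| 3 | 40% | 15/32 = 46.9% (29.1–65.3) | 12/29 = 41.4% (23.5–61.1) |
| 6 | 40% | 16/32 = 50.0% (31.9–68.1) | 10/26 = 38.5% (20.2–59.4) |
| 6 | 81% | 27/32 = 84.4% (67.2–94.7) | 21/26 = 80.8% (60.6–93.4) |

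**Step 4: one stratum.** If 32 patients split about equally, a stratum holds about 11 (an assumption). With 6 responders among 10 patients with marrow disease, one already-clear patient moves the rate from 6/10 = 60.0% to 7/11 = 63.6%.

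**The case against.** The strongest reply is that the wording already implies disease at the start. Relapsed/refractory normally means active leukaemia. The SAP says "The primary outcomes of interest are CR/CRi achieved or not following InO treatment which will be measured by binary response" and plans remission-free time from the start of InO, which presupposes patients who begin out of remission. This suggests the affected share may be small. It does not close the gap: the term is undefined, no marrow is required, and EMD/LBL patients can have active disease with a clear marrow.

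A second reply is that the study is descriptive and, at the only InO response rate the documents cite, the shift is small against sampling error. That stands for p near 81%. It is weaker if the real-world rate is lower, and SAP 7.2 puts the size of a measure ahead of statistical interpretation, so bias in that size matters.

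Three stronger readings are tempting, but the documents do not support them.
- **The 5% limit alone decides response, so patients just above it also become false responders.** CRi does waive count recovery, but CR and CRi both also require no evidence of marrow disease. A patient near the limit is not an automatic responder. Whether MRD-level disease counts as such evidence is not stated, so nothing here rests on it.
- **The bias is always upward.** By f(q−p), this holds only if already-clear patients are scored responders more often than the rest. If enough of them progress before the next marrow, the bias can be zero or negative.
- **The lack of a confirmatory marrow is a fault.** The documents do not say how many marrows are needed, and a chart review cannot impose one after the fact.

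**Conclusion.** The concern holds in a limited form. As written, the rules let a patient without marrow disease at index enter the primary denominator and be scored a CR/CRi responder without a drug effect. That follows from the text and needs no assumption.

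The size does rest on assumptions. If all such patients are scored responders, a 10% share inflates the rate by about 6 points at a true rate of 40% and 2 points at 81%; a 20% share gives about 12 and 4 points. The share could be near zero, in which case the effect is negligible. The plan as written would not report it. Distortion between salvage strata is possible, but the documents give no evidence of its direction or size.

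**What to change.** In Protocol section 3 and SAP 5.1 and 7.2:

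1. Compute the primary CR/CRi rate, overall and by salvage stratum, in patients with documented marrow disease: at least 5% blasts on the last marrow before InO, taken after the current relapse or refractory finding.
2. Show patients without marrow disease at index, and patients with no baseline marrow on record, in two separate rows with their counts.
3. Keep both groups in the cohort for survival, MRD and safety.
4. Report the all-patient rate as a sensitivity analysis.
5. State what relapsed and refractory mean for entry.

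The cost is some wording and two table rows. The blast result comes from the chart and is probably collected already for the burden subgroups, although those classes do not name marrow blasts. The primary denominator falls somewhat below 32, intervals widen a little, and the headline rate may be lower. Missing baseline marrows, which Protocol 9.7 makes likely, reduce it further; the separate row makes that loss visible.

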#### 9.1.2. Exclusion criteria

- Patient not completing at least 1 cycle of InO therapy
- Patient on InO in combination with chemotherapy

Following local legislation, informed consent won't be signed by the patients since this is a retrospective study and they are not getting enrolled in a prospective clinical trial. All data points mentioned in the inclusion criteria should be available which are necessary to analyze protocol endpoints for the selected patient cohort who has undergone the full treatment of the drug in question. Ethics Committee approval of study protocol will be taken to access medical records.

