# 4 ANALYSIS SETS/POPULATIONS

The population of interest will be the Relapsed/Refractory B Cell Acute lymphoblastic leukemia adult patients in India who had initiated and completed at least one cycle of InO monotherapy between Feb'2017 and Feb'2022 and CD22 positive.

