# 4.1 FULL ANALYSIS SET

The restrospective available record of all Relapsed/Refractory B Cell Acute lymphoblastic leukemia adult patients satisfying specified inclusion and exclusion criteria will be the full analysis set.

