# 4.2 SAFETY ANALYSIS SET

• Not required for this study

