# 4.3 OTHER ANALYSIS SET

• No other data set will be used for this study

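### Eligibility depends on completing cycle 1 of InO, but OS and RFS are timed from the start of cycle 1 and no all-starters analysis exists, so OS and CR/CRi (and, less strictly, RFS) are biased upward for patients treated with InO

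*Protocol*

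**What the plan says.** The Protocol's aim (Section 8) is "to observe clinical outcomes among patients treated with InO monotherapy in real-world clinical practice in India". Inclusion (Section 9.1.1) is by initiation of InO monotherapy, but Section 9.1.2 excludes a "Patient not completing at least 1 cycle of InO therapy". SAP Section 4 builds this into the population, as patients "who had initiated and completed at least one cycle of InO monotherapy between Feb'2017 and Feb'2022". Neither document defines what completing a cycle means.

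Protocol Section 3 sets the index date as "The date of initiation of the first cycle of InO" and OS as "Time from index date to death". RFS has the same origin, and SAP 5.1 likewise times death and relapse from the start of therapy. The CR/CRi rate in Protocol Section 3 is a proportion; its denominator is patients with a recorded InO discontinuation date.

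Under SAP 4.1, records "satisfying specified inclusion and exclusion criteria will be the full analysis set". For a safety set, SAP 4.2 says "Not required for this study". SAP 4.3 adds "No other data set will be used for this study". Neither document asks for a count of starters excluded for not completing cycle 1. Protocol 9.7 lists missing records, loss to follow-up, censoring and abstraction quality as limitations, but not this selection.

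**The concern.** Whether a patient enters the cohort is settled after the patient's clock has started. Someone who starts InO and dies in cycle 1, or stops in cycle 1 for toxicity or deterioration, never appears. Everyone who does appear was certain to be alive through cycle 1, and that time is credited as survival. This combines immortal time with selection on an early outcome.

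The primary endpoint (CR/CRi by number of prior salvage therapies) and the main survival endpoints are affected. Protocol 9.7 relies on Kaplan-Meier estimation to account for attrition from adverse events or lack of efficacy, but the earliest such attrition is deleted before any curve is drawn. Protocol Section 11 counts patients whose InO was interrupted for VOD/SOS, yet a patient whose VOD ended treatment within cycle 1 is outside the cohort. With the sample size reduced to 32 by the administrative change letter, a few missing patients can move a percentage noticeably.

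**Working it through.** The plan states no figure for this bias, so there is none to reproduce. What follows is an illustration.

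**Inputs from the documents:** median OS of 7.7 months with InO in the cited phase 3 trial and 6 months historically; 81% response with InO (all Protocol Section 7); N = 32 (administrative change letter).

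**Assumptions not in the documents:** constant hazard; these medians apply to all starters; cycle 1 lasts 21 to 28 days; completing a cycle means surviving all of it; the shares excluded and toxicity rates used in the response and toxicity steps.

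**Survival.** Let λ = ln 2 / median and c = cycle length in months (21/30.4375 = 0.690; 28/30.4375 = 0.920). The share of starters who die in cycle 1 is 1 − exp(−λc). Survival reported among completers is S(t)/S(c). With a constant hazard, the median among completers is the true median plus c.

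For a 7.7-month median, λ = 0.6931/7.7 = 0.0900 per month, S(0.690) = 0.940 and S(0.920) = 0.921.

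| Quantity | All starters | Completers, 21 days | Completers, 28 days |
|---|---|---|---|
| Removed by death in cycle 1 | none | 6.0% | 7.9% |
| 6-month survival | 58.3% | 0.583/0.940 = 62.0% | 0.583/0.921 = 63.3% |
| 12-month survival | 34.0% | 36.1% | 36.9% |
| Median OS, months | 7.7 | 8.4 | 8.6 |

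For a 6-month median, 7.7% to 10.1% are removed, and 6-month survival reads 54.1% to 55.6% instead of 50%.

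**Response.** If a share x of starters is excluded and none responded, a true rate p appears as p/(1 − x). For p = 70%, x of 5%, 10% or 15% gives 73.7%, 77.8% or 82.4%. In counts, 81% of 32 is about 26, and 26/32 = 81.3%. Restoring 2 excluded non-responders gives 26/34 = 76.5%; restoring 4 gives 26/36 = 72.2%. Removing 6.0% to 7.9% of starters to leave 32 corresponds to 32 × 0.060/0.940 = 2.0 to 32 × 0.079/0.921 = 2.7 patients.

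**Toxicity.** If the true rate is p and the excluded patients' rate is q, completers show (p − xq)/(1 − x). With p = 30% and x = 10%, the result is 22.2% for q = 100%, 26.7% for q = 60%, 30.0% for q = 30% and 33.3% for q = 0. The bias can go either way.

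**RFS.** Death in cycle 1, or stopping in cycle 1 because of global deterioration, is an RFS event that the exclusion removes. Progression alone is not an exclusion: a patient may progress, complete the cycle and count as an early event. The guaranteed interval is therefore not strictly free of RFS events.

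**The case against.** The best defence is that the selection is disclosed. SAP Section 4 openly names cycle-1 completers as the population, SAP 7.2 restricts extrapolation to patients who resemble the sample and calls interpretation qualitative, and SAP 3.1 states that no hypothesis is tested. That weakens any claim of concealment, but it does not repair the estimate. Completion is unknown when InO is started, so it cannot identify a patient group at that point, and limiting extrapolation does not move the time origin. The Section 8 aim still refers to patients treated with InO.

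The size is also uncertain, and this stands. If completing a cycle means only that its last dose was given, the guaranteed interval is shorter and the effect smaller. A shift of 4 to 5 points in 6-month survival is modest beside the sampling error at N = 32: around 62%, the approximate 95% half-width is 1.96 × √(0.62 × 0.38/32) = 17 points. But the confidence interval does not account for a systematic shift.

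A reader might infer that every outcome looks better. The documents do not support that. Dosage pattern, concomitant medication and cause of death have no favourable direction; DOR and cycles to CR/CRi concern responders and need not improve; VOD and Grade 3/4 rates can move either way. A reader might also infer that response has the same time-origin fault. The CR/CRi rate is a proportion, so its inflation comes through the denominator. Finally, a reader might infer that the contrast between salvage strata is compressed. That requires early loss to differ by stratum, and the documents give no such figures.

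**Conclusion.** The point holds for OS and CR/CRi, and less strictly for RFS: all are biased upward for patients treated with InO. The argument for OS rests on the documents' own definitions; for CR/CRi it also takes it that patients lost in cycle 1 seldom responded. Toxicity that ends treatment in cycle 1 goes unobserved, and the net direction for VOD and Grade 3/4 rates is uncertain.

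The size is illustrative only. Under a constant hazard, a 7.7-month median and a 3- to 4-week cycle, deaths alone remove about 6% to 8% of starters and raise 6-month survival from 58% to 62% or 63%. Stops for other reasons would remove further starters. The documents contain nothing that would fix the true figure, and as planned the report would not supply it either, because excluded starters are not counted.

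**What to change.** Preferred change:
- Delete the cycle-1 exclusion from Protocol 9.1.2 and the SAP 4.1 exclusion list, and redefine the SAP Section 4 population as patients who initiated InO monotherapy and received at least one dose.
- Make all starters the full analysis set for CR/CRi, OS, RFS, VOD and adverse events.
- In Protocol Section 3, change the CR/CRi denominator from patients with a recorded discontinuation date to all starters. Otherwise the primary endpoint has two conflicting denominators.
- Count starters who left before a response assessment as not in CR/CRi, and state this as an exception to the available-data rule in SAP Section 6.
- Remove the wording in Protocol 9.1.2 and SAP Section 5 that describes the cohort as having had the whole course of treatment.
- Keep cycle-1 completers as a secondary analysis.

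If the sponsor keeps the exclusion: define cycle completion, start OS and RFS at completion of cycle 1, label every result as applying to cycle-1 completers, report the number of excluded starters with reasons, and add the selection to Protocol 9.7. This corrects the time origin and discloses the selection, but does not recover outcomes for all treated patients.

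Cost of the preferred change: abstraction of a few more existing charts (about 2 to 3 beside 32 if only the deaths illustrated above are missing, more with other stops), a protocol amendment with IRB/IEC approval under Protocol 10.2, a matching SAP revision, and somewhat less favourable rates. The fallback needs no outcome data on the excluded patients beyond their number and reasons.
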